#### **IV. RESEARCH STUDY DESIGN**

---

**Overview and Design of the Proposed Study.** Consistent with our preliminary study, we will recruit (from the Denver and Boulder areas): 450 participants who report a desire to use marijuana to cope with their anxiety, have had previous experience with marijuana, and report a Generalized Anxiety Disorder-7 (GAD-7) score of  $\geq 5$  (at least mild to moderate anxiety) and 75 non-using cannabis controls (matched for anxiety via GAD-7  $\geq 5$ ) who do not report an intention to use marijuana to cope with their anxiety nor any marijuana use over the prior six months. A summary of the Assessment schedule and the additional inclusion/exclusion criteria are detailed below in Table 1 and Section VI (respectively).

All participants will come to the CUChange Lab for a Baseline Appointment (Session 1) involving extensive measures of anxiety (e.g., Depression, anxiety, and stress scale, a rumination induction task, a dot probe task, rumination self-report scale, etc.) and other psychiatric symptoms, health behavior (e.g., stress, quality of life, sleep, alcohol use), the cognitive testing battery utilized in our preliminary studies, a blood draw for biomarkers of inflammation, and a motor battery (**Baseline Appointment, Session 1**). During this Baseline Appointment, a research assistant will provide information on three at-home aspects of the study: 1) the range of assigned cannabis products (e.g., differing THC to CBD ratios possible) and potential prices, 2) the ActiGraph wearable watch device that participants will be loaned to measure physical activity and sleep (during the final 2 weeks of the four week study), and 3) a microbiome collection kit that they will be given to complete (once before and once after 4 weeks of *ad libitum* use of their cannabis product). The experimental aspect of this study will be the assigned cannabis ratio, while the other aspects of this study are *ad libitum* based, with regard to the dosing schedule and choice of product type (flower or edible), by participants that would already like to use cannabis to cope with their anxiety.

We are recruiting individuals who have indicated that they are unsure of what marijuana product to try and therefore want to try any of the ratios assigned in the study, would like to continue their typical strain use, or would like to change their strain to one of the ratios assigned in this study. We will ask that all subject inform of us of their subsequent strain purchased (assigned either strain C, D, or E), and the amount of cannabis purchased (not assigned) via an online short daily message (RedCap, provided as a CCTSI resource). Participants will then self-

administer the product as they see fit, without any instructions from study staff, for 4 weeks. Marijuana users (who according to our preliminary data, typically use marijuana with a THC potency of ~18%) will be assigned to use one of three strains with differing levels of THC and CBD. Considering the wide range of potencies, ratios, and types of cannabis products used, **we will assign one of three common flower cannabis ratios** [(THC:CBD = 1:0 (18/0%), 1:1 (12/12%), and 0:1 (0/18%)] and **one of three common edible cannabis ratios** [THC:CBD = 1:0 (10 mg), 1:1 (10/10 mg), or 0:1 (0/10 mg)]. Therefore, both flower and edible users will be identically assigned to +THC alone (1:0), a combination of +THC and +CBD (1:1), or +CBD alone (0:1), and will use their assigned product *ad libitum* (using as much or as little cannabis as they would like). Users will be advised to use their assigned cannabis product as they choose (i.e., their typical behavior), while non-users (control group) will be advised not to change their behavior and all groups will be instructed to report any change to us.

For cannabis user groups, we must recruit participants that have previously or currently used marijuana products and have a desire to continue or begin using any of the ratios and potencies potentially assigned during the study period. Thus, assignment to the all THC strain (+THC/-CBD, 1:0) serves as a naturalistic control group and our primary hypotheses surround effects of switching anxious marijuana users to either a strain with THC and CBD (e.g., +THC/+CBD, 1:1) or to a CBD-based strain without THC (i.e., -THC/+CBD, 0:1,), which are both likely to reduce anxiety symptoms over 4 weeks of use. Assessments occur at 2 and 4 weeks of *ad libitum* use, the typical time frame that symptom change would be detected from pharmacological treatment (e.g. SSRI). Details regarding marijuana strain assignment procedures, sample ascertainment, timing of assessments, power analyses, and the analytic plan follow.

As an exploratory endpoint, we will track participant's self-reported anxiety level, marijuana use, and sleep pattern with *daily follow-up messages* (online via email and the RedCap tool) over the course of the 4-week study period. This aspect will provide important data on patient choice, patient behavior, and edible impact on anxiety.

After the first two weeks (of four), all participants will return to the CINC (Creativity for Innovation & Creativity) laboratory (**2-Week Appointment, Session 2**) to complete the full set of biological measures and nearly all of the self-report measures and exercises with the elimination of one acute stressor (Rumination Induction) and the addition of one short survey on symptom change (Patient Global Impression of Change). After two more weeks (four weeks after the beginning of the study period), a final set of measures will be collected in our Mobile Van Pharmacology and Phlebotomy Laboratory (**4-Week Mobile Appointment: Pre & Post self-administration, Sessions 3 & 4**), to assess the longer/chronic (4-week, pre-administration, Session 3) and shorter/acute (0-1 hour, post-administration, Session 4) effects of cannabis use on all measures. Two additional measures will be added at this point to report the participant's current feelings after cannabis self-administration (Addiction Research Center Inventory (ARCI) and Drugs Effects Questionnaire (DEQ)).

While the main portion of the study will be complete after this 4-Week Appointment, we will continue to track participant's self-reported anxiety level, sleep pattern, and marijuana use with a *monthly follow-up survey* (online via email and the RedCap tool), over the course of a five-month follow-up, in keeping with the exploratory nature of the design. This aspect will provide important data on patient choice, patient behavior, and the effects of other marijuana products on anxiety.

In sum, the study will involve a 4 (marijuana-user groups: +THC/-CBD, , +THC/+CBD,, -THC/+CBD, and non-users) x 4 (Session: 1, 2, 3, and 4) mixed factorial design. The complete

schedule of assessments and measures taken at each assessment are outlined in Table 1 and described below.

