**Our global hypothesis is that the anxiolytic and inflammatory effects of marijuana vary as a function of the ratio of THC to CBD, and that these effects may shed light on the marijuana use/anxiety paradox.** The goal of this study is to test the effects of real-world, commercially-available, common marijuana products, that differ markedly in their ratio of THC to CBD [3 flower THC:CBD ratios (1:0, 1:1, or 0:1) and 3 edible THC:CBD ratios (1:0, 1:1, or 0:1) currently available]. To that end, we will test the effects of the following **marijuana ratios:** **1) +THC/-CBD (1:0), 2) +THC/+CBD (1:1), or 3) -THC/+CBD (0:1)** on anxiolytic,

inflammatory, and stress-reactivity processes. The first and last strains test the effects of THC and CBD in isolation, respectively, while the middle strain (+THC/+CBD) provide additional data on the effects of THC when CBD is also in blood, a critical comparison given our pilot data, suggesting that CBD mitigates the effects of THC.

**We will employ a design with marijuana users assigned to one of three (flower users) or one of three (edible users) marijuana strains (differing by ratio) for 4 weeks of ad-libitum cannabis use.** We will compare marijuana users to non-users (a matched control group), who are not assigned and do not use marijuana, and who do not have a desire to use marijuana to cope with their anxiety. Users, with a desire to self-administer marijuana to cope with their anxiety, will have the option to self-administer a flower (one of three ratios) or an edible (one of three ratios) cannabis product, however, each subject (regardless of their type of administration chosen) will be assigned to a product with +THC alone (1:0), a combinations of +THC and +CBD (1:1), or +CBD alone (0:1), and will use their assigned product ad libitum (using as much or as little cannabis as they would like).

**Aim 1:** To assess anxiety in mild to moderately anxious marijuana users exposed to one of three marijuana strains: 1) +THC/-CBD, 2)+THC/+CBD, or 3)-THC/+CBD compared to matched (non-using) controls.

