**Marijuana Administration at Home.** Unlike other studies done in the United States to date, the proposed work will utilize a design that allows participants to choose their type of administration and *ad libitum* dosing schedule, but contains an experimental element (i.e., strain assignment). Specifically, at the end of the baseline session, participants will be given instructions to purchase assigned strain, differing by THC to CBD ratio (n=75/flower strain; n=50/edible strain): 1) a THC-based strain akin to a typically used strain with normal levels of THC and little to no CBD (+THC/-CBD), 2) a 1:1 strain with equivalent THC and CBD levels (+THC/+CBD), or 3) a CBD-enriched strain with little to no THC (-THC/+CBD) at a good clinical practice dispensary in Boulder or Denver, Colorado.

The market for flower versus edible cannabis products are similar, but differ slightly in their servings, typical doses, and labeling system (potency listed by percent with flower products rather than by mg with edibles) making it currently impossible to assign identical flower and

edible potency groups, or ratios. However, Colorado requires all strains to be tested by a state licensed lab, which allows us to have a precise measure of potency to operationalize our strain assignments. Therefore, the flower groups will be assigned either the +THC/-CBD strain (containing 18% THC and <1% CBD), a combination of THC and CBD strain (a 1:1 ratio +THC/+CBD containing 12% THC and 12% CBD), or the -THC/+CBD strain (containing <1% THC and 18% CBD). Like the flower group, the edible groups will be assigned to one of the same ratios (an all THC strain, a combination of THC to CBD strain with a 1:1 ratio, or an all CBD strain) and they will choose when and how much they would like to use this assigned edible over the next four weeks. However, the participants that choose to be in the edible group (rather than the flower group), will be assigned an edible product with 10 mg of THC, CBD, or a combination of THC and CBD per edible piece (comparable to the flower products with 6, 12, or 18% THC, CBD, or a combination of THC and CBD).

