an all THC, all CBD, and a combination of THC to CBD group [(+THC/-CBD, +THC/+CBD, and -THC/+CBD, ratios: 1:0, 1:1, and 0:1)].

[figure not shown]
[figure not shown]
To be conservative, we thus estimated an ICC of .50. Using a mixed model ANOVA design, with four groups, three assessment points, and an average ICC = .5 between assessment points, a total  $n=450$  (75 per flower group and the control, and 50 per edible group) will allow us to detect a groupXtime interaction effect as small as  $f=.09$ . In **Aim 2B**, the test of the effects of group on stress-reactivity will again involve four groups ( 3 cannabis and 1 control) but only one assessment point.. Note that our power analysis is conservative, as our actual analysis will involve more powerful tests (e.g., focused interaction contrasts as opposed to overall  $F$  tests). For **Aim 3**, the estimation of the mediational model via path analysis (Hypothesis 3; see Figures 3a and 3b below), Monte Carlo simulation strategies formed the basis of our power analysis. Given that the model in Figure 3b is the more complex of the two, we utilized the model structure with the three planned contrasts as exogenous variables in our simulations. The key test of Hypothesis 3 will involve the use of structural equation modeling techniques. Because we have almost no empirical data on which to base estimates of effect size, we conservatively utilized small to moderate effect sizes depending upon hypothesized relationships. For example, we expect small coefficients (.20) from each contrast to stress reactivity, whereas we expect a slightly larger path (.40) between the contrast comparing the -THC/+CBD strain to control and inflammation. Power analyses were conducted in Mplus and then in SAS following procedures for estimating the power of the likelihood ratio test of the significance of parameters in structural equation models. We utilized Monte Carlo simulation to generate a population covariance matrix based on the hypothesized parameters in the model. For the smallest path in the model (which requires the most power to test), assuming two-tailed alpha of .05, our estimates of power at various sample sizes appear in Table 3. To assure .80 power or better to detect small associations between all groups, we thus require data from 450 participants (75 in the control and each flower group as well as 50 in each edible group) for our mediational analyses.

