**Specific Aim 1** – To compare changes in anxiety in mild to moderately anxious marijuana users exposed to 4 weeks of use of one of three different marijuana strains (+THC/-CBD vs. +THC/+CBD vs. -THC/+CBD) to a group of non-using controls matched on anxiety. *Hypothesis 1* predicts a main effect of strain such that -THC/+CBD marijuana users will have lower levels of anxiety (BAI) compared to other marijuana groups and to non-using controls. To examine the main effects of group on these outcomes, we will estimate a random coefficient regression (RCR) models in SAS Proc Mixed wherein the change in BAI scores will be regressed on marijuana user group, time, and the groupXtime interaction. *Hypothesis 1* also predicts that higher CBD levels in blood among marijuana users will be associated with lower BAI. The analysis for this hypothesis will again be a RCR model, but instead of group membership, the independent variables in these models will be level of CBD in blood, time, and the CBDxtime interaction. We will conduct additional models to explore whether there may also be main effects of THC in blood or a THCXCBD interaction effect on BAI. Secondary models will test the effects of strain and /or cannabinoid blood levels on the daily and monthly assessments of anxiety using a multi-level modeling approach. These additional analyses will appropriately control for Type I error, depending upon the number of tests run. Co-I [name] has used such models extensively in prior work.

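### The pooled 1:1 versus 1:0 contrast mixes two product changes (THC content falls in flower but not in edibles, as listed), so on its own it shows an assigned-ratio effect, not a CBD effect

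*Combined protocol and SAP*

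**What the plan says.** **Products.** The Overview in Section IV lists flower at "1:0 (18/0%), 1:1 (12/12%), and 0:1 (0/18" percent, THC first, and edibles at "1:0 (10 mg), 1:1 (10/10 mg), or 0:1 (0/10 mg" per piece. Marijuana Administration at Home repeats the flower figure, describing the combined strain as "a 1:1 ratio +THC/+CBD containing 12% THC and 12% CBD". That subsection also accepts that flower and edible potencies cannot be made identical.

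**Assignment.** Participants choose flower or edible. One of three ratios is then assigned within the chosen form, and they use as much or as little as they wish.

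**Analysis.** The Overview summarises the study as a "4 (marijuana-user groups: +THC/-CBD, , +THC/+CBD,, -THC/+CBD, and non-users) x 4 (Session: 1, 2, 3, and 4) mixed factorial design". The power analysis works "with four groups, three assessment points, and an average ICC = .5 between assessment points", although it gives sizes by form: "75 per flower group and the control, and 50 per edible group". In Aim 1, change in the Beck Anxiety Inventory (BAI) is "regressed on marijuana user group, time, and the groupXtime interaction". Aim 2A has the same structure, and Aim 2B uses group alone. No model has a product-form term or a form-specific contrast.

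**Purpose of the 1:1 arm.** The Objectives say that the combined strain will "provide additional data on the effects of THC when CBD is also in blood" and call this a critical comparison because pilot data suggest that CBD mitigates THC. Hypothesis 1 uses the same reasoning to predict less anxiety with 1:1 than with 1:0.

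**The concern.** One label, 1:1 versus 1:0, covers two different product changes. In flower, CBD is added and THC content is cut. In edibles, as the Overview lists them, CBD is added and THC content per piece stays the same. A four-group model averages the two.

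This matters because the protocol itself treats THC as acutely anxiogenic. Less THC is therefore a rival explanation, on the protocol's own terms, for lower anxiety in the 1:1 group. If the pooled contrast favours 1:1, it cannot by itself separate a benefit of CBD from a benefit of weaker THC in the flower arms.

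**Working it through.** **1. Change in product content, 1:0 to 1:1** (Overview, Section IV)

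- Flower THC: (12 − 18)/18 = −33%. Flower CBD: 0 to 12%.
- Edible THC: 10 mg to 10 mg, 0%. Edible CBD: 0 to 10 mg.

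**2. Weight of each form** (power analysis: 75 per flower group, 50 per edible group)

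- Each pooled ratio group: 75 + 50 = 125, of which 75/125 = 60% is flower.
- Average cut in THC content in the pooled contrast: 0.60 × 33% + 0.40 × 0% = 20%.

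**3. Does the power calculation pool over form?** The plan states a detectable group-by-time effect of f = .09 with N = 450, 3 assessments, ICC .5, two-sided alpha .05 and power .80. For the within-between interaction, λ = f²·N·m·ε/(1 − ρ), df1 = (k − 1)(m − 1)ε and df2 = (N − k)(m − 1)ε.

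| Groups k | ε | Power at f = .09 | Detectable f |
|---|---|---|---|
| 4 | 0.5 | 0.797 | 0.090 |
| 4 | 1 | 0.958 | 0.071 |
| 7 | 0.5 | 0.683 | 0.101 |
| 7 | 1 | 0.896 | 0.081 |

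The figure reproduces with four groups and ε = 0.5, and not with seven groups at either ε. The plan does not state ε, so this only supports what the text already says: four groups.

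**4. Detectable differences for 1:1 versus 1:0** (SD units, end-of-study means, 80% power, two-sided .05, no loss from the sizes above). By the normal approximation, d = (1.960 + 0.842) × √(2/n).

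- Pooled, 125 v 125: 2.802 × 0.1265 = 0.354
- Flower, 75 v 75: 2.802 × 0.1633 = 0.457
- Edible, 50 v 50: 2.802 × 0.2000 = 0.560
- Form × ratio interaction: 2.802 × √(2/75 + 2/50) = 2.802 × 0.2582 = 0.723

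The t distribution gives 0.356, 0.460 and 0.565 for the first three. A baseline covariate correlated .5 with the outcome would multiply these by √(1 − .25) = 0.866, so edible becomes 0.489. At a true difference of 0.354 SD, power is 0.80 pooled, 0.58 in flower and 0.43 in edibles. For an interaction of that size it is 0.28.

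**5. Possible size of the THC component (an assumption, not from the documents).** Suppose that removing all THC changes the outcome by b SD in flower users, the effect is linear in content, users do not adjust their intake and CBD does nothing. The flower contrast is then b/3 and the pooled contrast is 0.60 × b/3 = 0.20b.

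- b = 0.2: 0.04 SD
- b = 0.5: 0.10 SD
- b = 1.0: 0.20 SD

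Even 0.20 SD has only about 0.35 power at 125 v 125. The risk is a shifted estimate and a wrong label more than a false positive produced by THC alone.

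**6. Sensitivity to the edible description.** Marijuana Administration at Home describes each piece as having 10 mg of THC, of CBD or of the two combined, which can be read as 10 mg in total. On that reading the 1:1 piece would hold 5 mg THC, a 50% cut, and the average cut would be 0.60 × 33% + 0.40 × 50% = 40%. No form would then keep THC content constant.

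**The case against.** **The plan already separates THC from CBD through blood levels.** This is the strongest reply, and part of it stands. The rationale for the administration procedure names uncontrolled use as the design's weakness and answers it with continuous THC and CBD blood levels. Aims 1 and 2 include CBD-level models, with further models for THC and THC × CBD, and Aim 3 allows blood levels as predictors. A reader who infers that the plan ignores the distinction would be wrong. The limits are real, however. The main CBD model omits THC, and the THC and interaction terms are exploratory. Blood level is observed after assignment and is not randomised. The rationale claims to separate a CBD increase from a THC decrease only for the 0:1 strain. If the 24-hour abstinence instruction in the baseline procedures applies to later sessions, levels at Sessions 2 and 3 are residual.

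**Content is not dose.** This stands for both forms. Users of 12% flower may use more, and equal milligrams per piece do not fix THC intake in edibles. It makes the THC difference unknown; it does not turn the pooled contrast into a CBD contrast.

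**The edible arms isolate CBD, so any mitigation claim should rest on them alone.** A reader might infer this, but the documents do not support it. Intake is free, the edible content is described in two ways, and 50 v 50 has 0.43 power at the difference the pooled test detects with 0.80. Form is also self-chosen and differs in route and onset, so a flower-edible difference cannot be put down to THC content alone.

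**The randomised factor is the ratio.** Correct. The global hypothesis is about the THC-to-CBD ratio, and nowhere does the plan say that the pooled contrast will be reported as an isolated CBD effect. That reading is a risk created by the rationale, not a stated intention.

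**Form is balanced across ratios.** Also correct at 75:50 in each, so this is not baseline confounding. The issue is what the contrast means.

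**Conclusion.** The concern holds in this form: the pooled 1:1 versus 1:0 contrast is a valid comparison of assigned ratios, but alone it does not support a statement about CBD. It is 60% flower and carries an average 20% cut in THC content as the Overview lists the products. Under the assumptions in the working, the share of the pooled effect due to lower THC could be 0.04 to 0.20 SD for b between 0.2 and 1.0.

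Three things underlie this. Pooling is inferred from the four-group models and the absence of a form term, since the plan never says that it pools. The 20% figure depends on the Overview's edible contents. The argument is about content, because actual intake is unknown. It does not extend to saying that CBD effects cannot be studied here: the blood-level models contribute evidence, only not randomised evidence.

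**What to change.** 1. Add product form to the Aim 1 and 2 models, with strain × form (× time where measures repeat) as a supportive term. Non-users have no form, so code seven cells: user versus non-user (1 df), ratio (2), form (1) and ratio × form (2).
2. Keep the pooled test and describe it as an effect of assigned ratio.
3. Report 1:1 versus 1:0 by form as estimates with confidence intervals. State the detectable differences at 80% power (pooled about 0.36 SD, flower 0.46, edible 0.57, form × ratio interaction about 0.72), and note that form is self-chosen and differs in route.
4. State that CBD mitigates THC only with the form-specific results and the THC-adjusted blood-level results shown beside the claim.
5. Reconcile the Overview's edible contents with those in Marijuana Administration at Home, because constant THC content in edibles depends on the answer.

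The cost is wording in the analysis plan. Products, visits and sample size do not change, since ratio is already assigned and group sizes already set within form. The only balancing factor that the protocol states is sex, so form should be named explicitly in the model. The downside is precision: the form-specific intervals will be wider than the pooled one, and the interaction has little power.
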